10.8.8 Dose Range to be Investigated

Part A (SAD): No dose level that is predicted to exceed either the C_{max} or AUC₀₋₂₄ seen at the NOAEL in the nonclinical studies will be administered in this study without prior approval, via substantial amendment, from REC and MHRA. During the study, PK data from the previous cohort/s, along with safety and tolerability information, will be used to aid dose selection and the magnitude of the dose increase for the next cohort.

Part B (Food effect): The dose level at which the food effect will be performed will be based on a review of all available safety and PK data from Part A and will not exceed a dose tolerated in Part A.

Part C (MAD): The starting dose in Part C will not be expected to exceed the highest established AX-158 exposure (C_{max} and AUC_{0-24}) from Part A. Doses of AX-158 and matching placebo for Part C will be selected based on safety, tolerability and pharmacokinetic considerations from Part A (and where applicable previous cohort/s of Part C) which will be used to aid dose selection, magnitude of the dose increase for the next cohort and review of dosing regimen if appropriate. The maximum dose administered in a 24 h period will not exceed a level anticipated to result in a C_{max} or AUC_{0-24} exceeding those observed at NOAEL levels in nonclinical species without prior approval by the REC and MHRA (via substantial amendment).

10.8.9 Dose Escalation Increments

The planned dose escalation for all cohorts (with the exception of Part A [SAD] Cohort 1) is up to a 2-fold increase of the previous dose level. In Part A, it is planned to investigate up to 5 dose levels; however, it is possible that 2 additional dose level(s) may be investigated if justified based on available safety, tolerability, and PK data. In Part C, it is planned to investigate up to 3 dose levels; however, it is possible that 2 additional dose level(s) may be investigated if justified based on available safety and PK data. Dose escalation increments may vary from those planned but will not exceed 2-fold; the Sponsor and the Principal Investigator may decide not to proceed with further dose cohorts, to administer a lower or intermediate dose, to repeat a dose in subsequent cohorts or to proceed to a higher dose if at all. A dose level will not be repeated if dose escalation stopping criteria have been met at that dose level. It is noted that escalation/continuation to the next dose level will not occur if any individual participant's C_{max} or AUC_{0-24} data exceeds those levels seen at the NOAEL in the most sensitive preclinical species, (AX-158 C_{max} of 3.26 μ g/mL and AUC of 14.859 μ g*h/mL(males), or if they are anticipated to do so at the next dose level based on emerging PK data.

10.8.10 Timing of Dose for Each Participant

Participants will be required to fast for at least 10 h overnight prior to each morning dose. The fast will be broken 4 h after dosing with a light lunch (see [Section 10.6.5](#)). If the study is to be performed during fed conditions, it is recommended that participants should start the meal 30 minutes prior to administration of the drug product and eat this meal within 30 minutes. The caloric breakdown of the test meal should be provided in the study protocol, [Section 10.6.5](#).

For Part A (SAD) and Part C (MAD) two (2) dose leaders (1 active:1 placebo) will be dosed first in each cohort. The remainder of the cohort will be dosed at least 24 h later pending an acceptable safety profile in the dose-leader group.

10.8.11 Blinding

A designated individual from the IMP Management Department at Simbec-Orion will generate the randomisation code under the guidance of a statistician. All other site and Sponsor personnel involved in the study will be blinded with regards to the IMP being administered. The team responsible for the preparation of participant doses and emergency code break

envelopes will not be blinded and a copy of the original randomisation code will be issued to them for this purpose.

The Simbec-Orion Bioanalytical Scientist will be provided with a copy of the randomisation code for the purposes of analysing samples. The Bioanalytical Scientist will provide the drug concentration data for interim analysis and dose escalation data review in a re-coded participant number format, presented by dose level, in order to maintain the blind of study personnel.

The Simbec-Orion Pharmacology team members will be provided with a copy of the randomisation code for the purposes of PK analysis.

Participant doses: Once the randomisation code has been authorised as per Simbec-Orion SOPs, each participant dose will be packaged and labelled for individual participants by designated individuals from the IMP Management Department at Simbec-Orion on behalf of the Sponsor. The QP checks that the active drug and placebo are indistinguishable as part of the QP certification process.

Code break envelopes: Once the randomisation code has been authorised as per Simbec-Orion SOPs, the IMP Management team will produce individual sealed code-break envelopes that contain the treatment allocation(s) for each participant. The envelopes will be stored in a restricted access area. A set of code break envelopes will also be provided to the Simbec-Orion Pharmacovigilance (PV) Department.

Emergency unblinding: Where the site requires emergency access to an individual participant code Simbec-Orion will break the blind via the code break envelopes without prior consultation with the Sponsor. In such an event, the Sponsor will be notified as soon as possible via email.

Non-emergency unblinding: If an Investigator believes that knowledge of the IMPs received by a participant is essential for appropriate treatment of an AE, the code will be broken via the code break envelopes. Where practical, the Investigator should ideally consult the Sponsor before breaking the code. In any event, the Sponsor will be informed as soon as practical whenever the code has been broken for a participant.

If the blind needs to be broken for an individual participant, the date and reason will be recorded in the participant's eCRF. The Investigator will not reveal the unblinded treatment code to any other member of the clinical team involved in the study or to the Study Monitor. If the code is broken for any individual participant, the participant will be withdrawn from the study and the procedures accompanying withdrawal performed. If the code is broken without justification, this will be deemed a serious protocol deviation.

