10.7.4 Removal of Participants from Therapy or Assessment

Each participant will be informed of their right to withdraw from the study at any time and for any reason.

An Investigator will withdraw a participant from the study at any time for any of the following reasons:

- If a participant experiences a serious or intolerable AE, that prevents them from continuing.
- If a participant incurs a significant protocol violation which impacts on their safety or the scientific integrity of the study (this will be discussed on a case-by-case basis with the sponsor).
- At the request of the Sponsor.
- If it is considered that the participant's health is compromised by remaining in the study or the participant is not sufficiently cooperative.
- If a participant is lost to follow-up.

The reasons for any participant withdrawal will be recorded on the study completion form of the electronic case report form (eCRF).

If a participant is withdrawn or chooses to withdraw from the study for any reason every possible effort will be made to perform the evaluations described for the post-study follow-up (see **Table 10.9.1**, **Table 10.9.2** and **Table 10.9.3**). The data collected from withdrawn participants will be included in the study report.

In the event of any abnormalities considered to be clinically significant, participants will be followed-up with appropriate medical management until values are considered to be clinically acceptable. Referral or collaborative care will be organised if considered necessary.

Up to one hundred and four (104) participants are planned to be enrolled into the study. Participants who withdraw from the study before receiving any IMP will be replaced. Participants who are withdrawn from the study due to significant drug-related AEs will not be replaced. Replacement of all other participants withdrawn from the study after receiving IMP will be decided on a case-by-case basis by the Principal Investigator (or deputy) and Sponsor.

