| 6 | Pre dose on Day 7 only |
| 7 | Total serum testosterone required at screening, pre dose D-1 and on D11 |
| 8 | Serum LH required at pre dose (D-1) and on D11 |
| 9 | Vital signs include the following assessments: supine systolic and diastolic blood pressure, supine heart rate, respiration rate and oral temperature |
| 10 | 12-lead ECG will be performed at screening, pre-dose and at 30 min, 4 h, 12 h, 24 h, 48 h and 72 h post-dose Days 1 and 10 and at the post-study follow up visit. |
| 11 | For all cohorts IMP or placebo will be administered orally in a fasted state (after an overnight fast of at least 10 h) with 240 mL water. The fast will be broken 4 h post-dose with lunch on Days 1-10. |
| 12 | Urine sampling: for AX-158: pre-dose and in intervals of 0-12, 12-24, 24-48 and 48-72 h post-dose on Day 1 and Day 10 |
| 13 | Symptom Directed |
| 14 | Pre-dose trough sample day 5 only |
| 15 | COVID-19 test on day 8 and prior to check out. |
| 16 | Additional samples will be taken based on emerging data |

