11.6.2 Laboratory Data

Routine safety clinical laboratory tests (biochemistry, hematology, coagulation, urinalysis) will be carried out at:

Part A: Screening, Day -1, 24h post dose, 72h post dose and at follow-up. An additional urinalysis test will be carried out at Day 1, 12h.

Part B: Screening, Day -1, 24h post dose, 72h post dose and at follow-up. An additional biochemistry test will be carried out at Day 1 pre dose (total serum testosterone only) and an additional urinalysis test will be carried out at Day 1 – 12h.

Part C: Screening, Day -1, 24h post dose, 72h post dose, pre-dose on Day 5 and at follow-up. An additional biochemistry test (total serum testosterone and LH only) will be carried out at Day 1 pre-dose, Day 5, Day 8 and Day 11 and an additional urinalysis test will be carried out at Day 1, 12h.

The laboratory parameters required for this study are listed in section 9.2.1.

Laboratory data listings will be presented in two ways:

- Out of range values - any values that fall outside of the normal/alert ranges based on the reference ranges provided by the Simbec-Orion Laboratory Services (presented in listing format within the data summaries)
- All safety laboratory data (including physician's review (Normal, Abnormal-NCS, Abnormal-CS)) with any out of range values flagged (presented within the data listings).

Descriptive statistics (N, n, mean, SD, minimum, median and maximum) of absolute and change from baseline (last assessment prior to first dose within a treatment period) values for each parameter at each protocol defined time point will be tabulated by treatment.

Microscopy, virology, COVID-19 test, urine drugs of abuse and alcohol screen and any unplanned laboratory parameters will also be listed.

If there are no further parameters databased other than those specified in section 9.2.1 then the 'Other Laboratory Data' listings should display, 'No other laboratory parameters to report'.

Laboratory data will be listed and summarised using the Safety Set.

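### A code break ends the required PK and serial safety assessments in that participant, although escalation depends on each individual's exposure

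*Protocol*

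**What the plan says.** Protocol section 10.8.11 allows the code to be broken in an emergency, or when an investigator needs to know the allocation to treat an AE. The consequence is the same in every case: "If the code is broken for any individual participant, the participant will be withdrawn from the study and the procedures accompanying withdrawal performed".

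Section 10.7.4 has a separate, conditional rule for AEs: "If a participant experiences a serious or intolerable AE, that prevents them from continuing". For anyone withdrawn for any reason, "every possible effort will be made to perform the evaluations described for the post-study follow-up". It adds that "The data collected from withdrawn participants will be included in the study report" and that, for clinically significant abnormalities, "participants will be followed-up with appropriate medical management until values are considered to be clinically acceptable". Participants withdrawn for significant drug-related AEs are not replaced.

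On escalation, section 10.8.9 says that "escalation/continuation to the next dose level will not occur if any individual" participant's Cmax or AUC0-24 exceeds the limits of 3.26 µg/mL and 14.859 µg·h/mL. Section 10.3.1 requires at least 6 evaluable participants from the preceding dose level. To be evaluable, a participant needs enough PK samples to estimate Cmax and AUC0-24.

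For laboratory tests, SAP section 11.6.2 gives "Part A: Screening, Day -1, 24h post dose, 72h post dose and at follow-up". Footnote 9 to protocol Table 10.9.1 includes an ECG at follow-up. No part of the study has a PK sample at follow-up.

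**The concern.** The protocol treats stopping IMP, being unblinded and leaving the study as one event. The SAP does the same in section 11.6.1, where a TEAE leading to study withdrawal is identified by study drug having been discontinued. In Part A the single dose has already been given, so withdrawal after dosing prevents no exposure. Its effect is on what is still collected.

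The participant most likely to be unblinded or withdrawn early is one with a troublesome reaction, so the missing data are informative. If his PK profile stops early, his Cmax or AUC0-24 may never be known, and a value that was never measured cannot breach the individual limit in section 10.8.9. Serial ECG and laboratory summaries at later time points would then describe mainly those who tolerated the dose. Safety is the primary objective, and SAP section 10.4 has no method for missing safety data.

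**Working it through.** **Inputs.** Part A PK times (SAP section 11.4.1): pre-dose, 0.5, 0.75, 1, 2, 3, 4, 6, 8, 12, 24, 36, 48 and 72 h, so 14 samples. Check against protocol Table 10.9.4: 14 × 4.0 mL = 56.0 mL, as stated there. Post-dose ECGs (Table 10.9.1, footnote 9): 0.5, 4, 12, 24, 48 and 72 h plus follow-up, so 7. Post-dose biochemistry, haematology and coagulation panels: 24 h, 72 h and follow-up, so 3.

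**Assumption.** The documents give no withdrawal time or rate, so a range is shown. Withdrawal at time t means that the assessment due at t has been done. The number no longer required is the count of scheduled times later than t, with the follow-up ECG and panel treated as still obtained.

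| Assumed withdrawal | PK no longer required (of 14) | Of these, at or before 24 h | ECGs (of 7) | Laboratory panels (of 3) |
|---|---|---|---|---|
| 1 h | 10 | 7 | 5 | 2 |
| 4 h | 7 | 4 | 4 | 2 |
| 12 h | 4 | 1 | 3 | 2 |
| 24 h | 3 | 0 | 2 | 1 |

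Observed AUC0-24 is incomplete only for withdrawal before 24 h. Cmax is at risk only if withdrawal comes before the peak. As this is a first-in-human study, the protocol has no observed human Tmax with which to place that.

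**Effect on the escalation rule.** One active participant is 1/6 = 17% of the active PK profiles in a cohort of 8. If he is not evaluable, 8 − 1 = 7 remain. The threshold of 6 is still met, and escalation can be considered without his exposure. SAP section 3.1 gives 6 participants in Part A cohorts 2, 3 and 4. There 6 − 1 = 5, so the threshold would be missed and the same loss would hold up escalation.

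**Part C.** Serial PK to 72 h is scheduled only after Days 1 and 10. A participant stopped after the Day 3 dose already has his Day 1 Cmax and AUC0-24. For hormones, protocol Table 10.9.3 says "Total serum testosterone required at screening, pre dose D-1 and on D11", and its LH footnote gives Day -1 and D11. He would therefore have no on-treatment testosterone or LH. The SAP adds Day 5 (section 3.4.1) and Day 8 (section 11.6.2), and both also fall after that stop. Testicular change was one of the toxicology findings in protocol section 8.5.

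**The case against.** Several safeguards narrow the point.

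- A reader might infer that any serious or intolerable AE removes the participant. Section 10.7.4 does not say this: the AE must also prevent him from continuing. Only the code-break rule is unconditional.
- A reader might infer that ECG and laboratory data are lost altogether. They are not. Follow-up includes both, data already collected are reported, and significant abnormalities are followed under sections 10.7.4 and 10.9.16. Footnote 2 to Table 10.9.4 foresees unscheduled tests. Section 10.6.3 expects participants to stay in the unit until 24 h after the last dose, which makes early sampling practicable. What lapses is the requirement for the scheduled serial assessments.
- A reader might infer that escalation could proceed unchecked after a serious reaction. Section 10.3.4 prevents this. One serious related reaction, or one severe and at least possibly related AE in ECG, laboratory or vital signs that may jeopardise safety, halts dosing or escalation. Escalation then needs an approved substantial amendment. The exposed gap is mainly a code break or withdrawal within 24 h that does not meet those criteria.
- A reader might infer that the SAP discards data after a code break. It does not. The Safety Set (section 6.2) is every randomised participant dosed at least once, and the PK Set criteria (section 6.3) contain no code-break exclusion. A Part C participant with a valid Day 1 profile may stay in the PK Set.

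All of this stands and limits the size of the problem. It does not remove it, because nothing requires the remaining PK profile in the person whose exposure is of most interest.

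**Conclusion.** The point holds as a gap in required data collection. Section 10.8.11 withdraws every code-broken participant, section 10.7.4 then requires only follow-up evaluations, and section 10.8.9 relies on individual exposure that those evaluations cannot supply. The three sections should be reconciled.

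In Part A between 3 and 10 of 14 PK samples are no longer required for withdrawal between 24 h and 1 h, and AUC0-24 is affected only before 24 h. These counts rest on assumed withdrawal times and on the site doing no more than the protocol requires. How often this would happen cannot be estimated from the documents. It is a worthwhile, inexpensive improvement, and the documents do not support calling it a failure of the escalation safeguards.

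The SAP is written to protocol version 5.0 (15 March 2022), whereas the protocol reviewed is version 4.0. The wording should be checked in the later version before acting.

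**What to change.** In protocol sections 10.7.4 and 10.8.11, state that unblinding or stopping IMP does not by itself end data collection. With continuing consent, and where medically feasible, the participant completes the remaining PK and safety assessments already scheduled, then the follow-up visit. Say expressly that this concerns data collection only and does not alter who stops IMP or when. Align section 10.8.9 by cross-reference.

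In Part C, collect what is already scheduled. PK to 72 h after an unplanned last dose would be a new procedure and is not proposed. Running testosterone and LH on the existing follow-up biochemistry sample is an optional small addition.

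The SAP needs no change to its analysis sets, only a sentence confirming that data obtained after a code break are kept.

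The cost is protocol wording, with the amendment classified under section 11.2, and a longer stay or a return visit for some participants.

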10.8.12 Prior and Concomitant Therapy

Prior Medication: Prescription or non-prescription drugs, including vitamins, herbal and dietary supplements should not be taken within 28 days (or 5 half-lives (whichever is longer)) prior to the first dose of IMP, unless in the opinion of the Investigator and Sponsor's Responsible Physician the medication will not interfere with the study procedures or compromise participant safety. Prescription or non-prescription drugs, including vitamins, herbal and dietary supplements taken during the 28 days before the first dose of IMP, and the reason for taking them, will be noted in the participant's eCRF.

Participants should not receive a COVID-19 vaccine within 28 days prior to the first dose of IMP.

Inclusion of participants who have taken prior medication will be reviewed on a case-by-case basis in relation to the safety aspects and objectives of this study.

Concomitant Medication: Prescription or non-prescription drugs, including vitamins, herbal and dietary supplements should not be taken throughout the duration of the study, with the exception of paracetamol (which may be taken as an analgesic to a maximum of 2g in 24 h).

Participants should not receive a COVID-19 vaccine from the first dose of IMP to completion of the post-study follow up visit.

If intake of any prior or concomitant medication is necessary during the study, the daily dosage, duration, and reasons for administration will be recorded on the participant's eCRF.

10.8.13 Treatment Compliance

Each dose of IMP will be taken under supervision and a hand and mouth check conducted. The exact dosing time for each participant will be recorded on the participant's eCRF.

10.9 Efficacy and Safety Variables

10.9.1 Efficacy and Safety Measurements Assessed and Flow Chart

A schedule of study assessments is provided in [Table 10.9.1](#), [Table 10.9.2](#) and [Table 10.9.3](#). Simbec-Orion personnel who have been appropriately trained will carry out study procedures. Where more than 1 procedure is scheduled for the same time-point, the following order of priority will apply:

1. PK blood sampling. Blood samples collected outside of the defined deviation windows will be recorded as protocol deviations: \pm 1 minute for samples collected up to 45 minutes time-point (inclusive) and \pm 5 minutes for samples collected $>$ 45 minutes time-point.
2. Vital signs and 12-lead ECG (a window of \pm 10 min in relation to the nominal time-point is allowed).
3. Start or finish of urine collection interval (a window of \pm 10 min in relation to the nominal time-point).

All baseline assessments may be performed within the 1 h before dosing.

Table 10.9.1 Study Flow Chart – Part A Single Ascending Dose

| Visits ^{1,2} | Screening | Treatment Period | | | | | | | | | | | | | | Follow up | |
|---|----------------|------------------|----------|---|-----|------|----|----|----|----|----|----|--------------------------|--------------------------|--------------------------|-----------------------------|-----------------|
| | | In-house | | | | | | | | | | | | | | | |
| Days | Day – 28 to -2 | Day - 1 | Day 1 | | | | | | | | | | Post-Treatment 1 (Day 2) | Post-Treatment 2 (Day 3) | Post-Treatment 3 (Day 4) | 5-7 days from last IMP dose | |
| Time (h) | | | Pre-Dose | 0 | 0.5 | 0.75 | 1h | 2h | 3h | 4h | 6h | 8h | 12h | 24h | 36h | 48h | 72h |
| Informed Consent | X | | | | | | | | | | | | | | | | |
| Inclusion/Exclusion ³ | X | X | X | | | | | | | | | | | | | | |
| Demographics | X | | | | | | | | | | | | | | | | |
| Height/Weight/BMI ⁴ | X | X | | | | | | | | | | | | | | | |
| Medical History & Concurrent Conditions | X | | | | | | | | | | | | | | | | |
| Virology Tests (HIV, HBsAg, HCV) | X | | | | | | | | | | | | | | | | |
| Drug and Alcohol Screen ⁵ | X | X | | | | | | | | | | | | | | | |
| COVID-19 Test | X | | | | | | | | | | | | | | | | |
| Biochemistry | X ⁶ | X | | | | | | | | | | | X | | | X | X |
| Haematology | X | X | | | | | | | | | | | X | | | X | X |
| Urinalysis | X | X | | | | | | | | | | | X | X | | X | X |
| Coagulation ⁷ | X | X | | | | | | | | | | | X | | | X | X |
| Randomisation | | X | | | | | | | | | | | | | | | |
| Adverse Events | X | X | X | X | X | X | X | X | X | X | X | X | X | X | X | X | X |
| Vital Signs ⁸ | X | X | X | | X | X | X | X | X | X | X | X | X | X | X | X | X |
| Physical Examination | X | X ¹¹ | | | | | | | | | | | | | | X ¹¹ | X ¹¹ |
| 12-Lead ECG ⁹ | X | X | X | | X | | | | X | | | X | X | | X | X | X |

| Visits ^{1,2} | Screening | Treatment Period | | | | | | | | | | | | | | Follow up | |
|--------------------------------|----------------|------------------|-----------------|---|-----|------|----|----|----|----|----|----|--------------------------|--------------------------|--------------------------|-----------------------------|-----|
| | | In-house | | | | | | | | | | | | | | | |
| Days | Day – 28 to -2 | Day -1 | Day 1 | | | | | | | | | | Post-Treatment 1 (Day 2) | Post-Treatment 2 (Day 3) | Post-Treatment 3 (Day 4) | 5-7 days from last IMP dose | |
| Time (h) | | | Pre-Dose | 0 | 0.5 | 0.75 | 1h | 2h | 3h | 4h | 6h | 8h | 12h | 24h | 36h | 48h | 72h |
| Prior & Concomitant Medication | X | X | X | X | X | X | X | X | X | X | X | X | X | X | X | X | X |
| Dose IMP ¹⁰ | | | X | | | | | | | | | | | | | | |
| Blood Sampling for PK | | | X | | X | X | X | X | X | X | X | X | X | X | X | X | |
| Exploratory PD sample | | | X ¹² | | | | | | | | | | | | | | |

Study Flow Chart Footnotes:

- 1 All cohorts will complete only 1 Treatment Period.
- 2 Participants will be in the clinical unit for their in-house period from the morning before dosing (Day -1), until the completion of all the assessments on Post-Treatment 3 (Day 4).
- 3 Eligibility will be determined during screening. Continued eligibility will be confirmed on Day -1, and pre-dose Day 1.
- 4 Height measured at Screening only.
- 5 A urine sample will be used to screen for drugs of abuse (including alcohol and cotinine).
- 6 Total serum testosterone only required at screening.
- 7 Coagulation testing aPTT and PT
- 8 Vital signs include the following assessments: supine systolic and diastolic blood pressure, supine heart rate, respiration rate and oral temperature
- 9 12-lead ECG will be performed at screening, each period pre-dose and at 30 min, 4 h, 12 h, 24 h, 48 h and 72 h post-dose and at the post-study follow up visit.
- 10 IMP or placebo will be administered orally in a fasted state (after an overnight fast of at least 10 h) with 240 mL water. The fast will be broken 4 h post-dose with lunch.
- 11 Symptom directed
- 12 Cohort 3 onwards additional samples will be taken based on emerging data

Table 10.9.2 Study Flow Chart – Part B Food Effect

| Visits ^{1,2} | Screening | Treatment Periods 1 & 2 | | | | | | | | | | | | | | Follow up | |
|---|----------------|-------------------------|----------|---|-----|------|----|----|----|----|----|----|--------------------------|--------------------------|--------------------------|-----------------------------|-----------------|
| | | In-house | | | | | | | | | | | | | | | |
| Days | Day – 28 to -2 | Day -1 | Day 1 | | | | | | | | | | Post-Treatment 1 (Day 2) | Post-Treatment 2 (Day 3) | Post-Treatment 3 (Day 4) | 5-7 days from last IMP dose | |
| Time (h) | | | Pre-Dose | 0 | 0.5 | 0.75 | 1h | 2h | 3h | 4h | 6h | 8h | 12h | 24h | 36h | 48h | 72h |
| Informed Consent | X | | | | | | | | | | | | | | | | |
| Inclusion/Exclusion ³ | X | X | X | | | | | | | | | | | | | | |
| Demographics | X | | | | | | | | | | | | | | | | |
| Height/Weight/BMI ⁴ | X | X | | | | | | | | | | | | | | | |
| Medical History & Concurrent Conditions | X | | | | | | | | | | | | | | | | |
| Virology Tests (HIV, HBsAg, HCV) | X | | | | | | | | | | | | | | | | |
| Drug and Alcohol Screen ⁵ | X | X | | | | | | | | | | | | | | | |
| COVID-19 Test | | X | | | | | | | | | | | | | | | |
| Biochemistry | X ⁶ | X | | | | | | | | | | | X | | | X | X |
| Haematology | X | X | | | | | | | | | | | X | | | X | X |
| Urinalysis | X | X | | | | | | | | | | | X | X | | X | X |
| Coagulation ⁷ | X | X | | | | | | | | | | | X | | | X | X |
| Randomisation | | | X | | | | | | | | | | | | | | |
| Adverse Events | X | X | X | X | X | X | X | X | X | X | X | X | X | X | X | X | X |
| Vital Signs ⁸ | X | X | X | | X | X | X | X | X | X | X | X | X | X | X | X | X |
| Physical Examination | X | X ¹¹ | | | | | | | | | | | | | | X ¹¹ | X ¹¹ |
| 12-Lead ECG ⁹ | X | X | X | | X | | | | | X | | | X | X | | X | X |
| Prior & Concomitant Medication | X | X | X | X | X | X | X | X | X | X | X | X | X | X | X | X | X |
| Dose IMP ¹⁰ | | | | X | | | | | | | | | | | | | |

| Visits ^{1,2} | Screening | Treatment Periods 1 & 2 | | | | | | | | | | | | | | Follow up | |
|-----------------------|----------------|-------------------------|----------|---|-----|------|----|----|----|----|----|----|--------------------------|--------------------------|--------------------------|-----------------------------|-----|
| | | In-house | | | | | | | | | | | | | | | |
| Days | Day – 28 to -2 | Day -1 | Day 1 | | | | | | | | | | Post-Treatment 1 (Day 2) | Post-Treatment 2 (Day 3) | Post-Treatment 3 (Day 4) | 5-7 days from last IMP dose | |
| Time (h) | | | Pre-Dose | 0 | 0.5 | 0.75 | 1h | 2h | 3h | 4h | 6h | 8h | 12h | 24h | 36h | 48h | 72h |
| Blood Sampling for PK | | | X | | X | X | X | X | X | X | X | X | X | X | X | X | |

Study Flow Chart Footnotes:

| | |
|----|---|
| 1 | All cohorts will complete Treatment Period 1 & 2. |
| 2 | For Treatment Periods 1 & 2, participants will be in the clinical unit for their in-house period from the morning before dosing (Day -1), until the completion of all the assessments on Post-Treatment 3 (Day 4). |
| 3 | Eligibility will be determined during screening. Continued eligibility will be confirmed on Day -1, and pre-dose Day 1 for Treatment Periods 1 & 2. |
| 4 | Height measured at Screening only. |
| 5 | A urine sample will be used to screen for drugs of abuse (including alcohol and cotinine). |
| 6 | Total serum testosterone only required at screening. |
| 7 | Coagulation testing aPTT and PT |
| 8 | Vital signs include the following assessments: supine systolic and diastolic blood pressure, supine heart rate, respiration rate and oral temperature |
| 9 | 12-lead ECG will be performed at screening, each period pre-dose and at 30 min, 4 h, 12 h, 24 h, 48 h and 72 h post-dose and at the post-study follow up visit. |
| 10 | Participants will receive a single dose of AX-158 following an overnight fast of at least 10 h OR following consumption of a high-fat breakfast over 2 treatment periods (1 per period). AX-158 should be administered 30 mins after the start of the meal. |
| 11 | Symptom directed |

Table 10.9.3 Study Flow Chart – Part C Multiple Ascending Dose

| Visits ¹ | Screening | In-house | | | | | | | | | | | | | | | Follow up | |
|---|----------------|------------------|----------------|---------|----------------------------------|----|----|----|----|----|-----|------------------|-----|-----|-----------------|-----------------|-----------------|---|
| | | Days | Day - 28 to -2 | Day - 1 | Day 1-4, Day 10-13 ¹⁵ | | | | | | | | | | | | | |
| Time (h) | Pre-Dose | 0 | 0.5 | 0.75 | 1h | 2h | 3h | 4h | 6h | 8h | 12h | 24h | 36h | 48h | 72h | | | |
| Informed Consent | X | | | | | | | | | | | | | | | | | |
| Inclusion/Exclusion ² | X | X | X | | | | | | | | | | | | | | | |
| Demographics | X | | | | | | | | | | | | | | | | | |
| Height/Weight/BMI ³ | X | X | | | | | | | | | | | | | | | | |
| Medical History & Concurrent Conditions | X | | | | | | | | | | | | | | | | | |
| Virology Tests (HIV, HBsAg, HCV) | X | | | | | | | | | | | | | | | | | |
| Drug and Alcohol Screen ⁴ | X | X | | | | | | | | | | | | | | | | |
| COVID-19 Test | | X | | | | | | | | | | | | | | X ¹⁵ | | |
| Biochemistry | X ⁷ | X ^{7,8} | | | | | | | | | | X ^{7,8} | | | X | X ⁶ | X | |
| Haematology | X | X | | | | | | | | | | X | | | X | X ⁶ | X | |
| Urinalysis | X | X | | | | | | | | | X | X | | | X | X ⁶ | X | |
| Coagulation ⁵ | X | X | | | | | | | | | X | | | | X | X ⁶ | X | |
| Randomisation | | X | | | | | | | | | | | | | | | | |
| Adverse Events | X | X | X | X | X | X | X | X | X | X | X | X | X | X | X | X | X | |
| Vital Signs ⁹ | X | X | X | | X | X | X | X | X | X | X | X | X | X | X | X ⁶ | X | |
| Physical Examination | X | X ¹³ | | | | | | | | | | | | | X ¹³ | | X ¹³ | |
| 12-Lead ECG ¹⁰ | X | X | X | | X | | | | X | | | X | X | | X | X | X ⁶ | X |
| Prior and Concomitant Medication | X | X | X | X | X | X | X | X | X | X | X | X | X | X | X | X | X | |
| Dose IMP ¹¹ | | | X | | | | | | | | | X | | X | X | X | | |
| Blood Sampling for PK | | | X | | X | X | X | X | X | X | X | X | X | X | X | X ¹⁴ | | |

| Visits ¹ | Screening | In-house | | | | | | | | | | | | | | Follow up | | | |
|-----------------------|----------------|----------|----------------------------------|--------|-----|------|----|----|----|----|----|----|-----|-----|-----|-----------|-----------------------------|--|--|
| Days | Day - 28 to -2 | Day - 1 | Day 1-4, Day 10-13 ¹⁵ | | | | | | | | | | | | | Day 5-9 | 5-7 days from last IMP dose | | |
| Time (h) | | | Pre-Dose | 0 | 0.5 | 0.75 | 1h | 2h | 3h | 4h | 6h | 8h | 12h | 24h | 36h | 48h | 72h | | |
| Urine Sampling for PK | | | X ¹² | ←————→ | | | | | | | | | | | | | | | |
| Exploratory PD sample | | | X ¹⁶ | | | | | | | | | | | | | | | | |

Study Flow Chart Footnotes:

| | |
|----|---|
| 1 | For each cohort participants will be in the clinical unit for their inpatient visit from the morning before dosing (Day -1), until the completion of all assessments on Day 13. |
| 2 | Eligibility will be determined during screening. Continued eligibility will be confirmed on Day -1, and pre-dose Day 1-10 |
| 3 | Height measured at Screening only. |
| 4 | A urine sample will be used to screen for drugs of abuse (including alcohol and cotinine). |
| 5 | Coagulation testing aPTT and PT |
| 6 | Pre dose on Day 7 only |
| 7 | Total serum testosterone required at screening, pre dose D-1 and on D11 |
| 8 | Serum LH required at pre dose (D-1) and on D11 |
| 9 | Vital signs include the following assessments: supine systolic and diastolic blood pressure, supine heart rate, respiration rate and oral temperature |
| 10 | 12-lead ECG will be performed at screening, pre-dose and at 30 min, 4 h, 12 h, 24 h, 48 h and 72 h post-dose Days 1 and 10 and at the post-study follow up visit. |
| 11 | For all cohorts IMP or placebo will be administered orally in a fasted state (after an overnight fast of at least 10 h) with 240 mL water. The fast will be broken 4 h post-dose with lunch on Days 1-10. |
| 12 | Urine sampling: for AX-158: pre-dose and in intervals of 0-12, 12-24, 24-48 and 48-72 h post-dose on Day 1 and Day 10 |
| 13 | Symptom Directed |
| 14 | Pre-dose trough sample day 5 only |
| 15 | COVID-19 test on day 8 and prior to check out. |
| 16 | Additional samples will be taken based on emerging data |

